5.1.3 Target Lesions

All measurable lesions up to a maximum of five lesions per organ and 10 lesions in total representative of all involved organs should be identified as target lesions and recorded and measured at baseline. Target lesions should be selected on the basis of their size (lesions with the longest diameter) and their suitability for accurate repeated measurements (either by imaging techniques or clinically). A sum of the longest diameter (LD) for all target lesions will be calculated and reported as the baseline sum LD. The baseline sum LD will be used as reference by which to characterize the objective tumor response.

5.1.4 Non-Target Lesions

All other lesions (or sites of disease) should be identified as non-target lesions and should also be recorded at baseline. Non-target lesions include measurable lesions that exceed the maximum numbers per organ or total of all involved organs as well as non-measurable lesions. Measurements of these lesions are not required, but the presence or absence of each should be noted throughout follow-up.

5.2 Guidelines for Evaluation of Measureable Disease

All measurements should be taken and recorded in metric notation using a ruler or calipers. All baseline evaluations should be performed as closely as possible to the beginning of treatment and never more than 4 weeks before the beginning of the treatment.

The same method of assessment and the same technique should be used to characterize each identified and reported lesion at baseline and during follow-up. Imaging-based evaluation is preferred to evaluation by clinical examination when both methods have been used to assess the antitumor effect of a treatment.

5.2.1 Clinical lesions

Clinical lesions will only be considered measurable when they are superficial (e.g., skin nodules and palpable lymph nodes). In the case of skin lesions, documentation by color photography, including a ruler to estimate the size of the lesion, is recommended.

5.2.2 Cytology, Histology

These techniques can be used to differentiate between partial responses (PR) and complete responses (CR). The cytological confirmation of the neoplastic origin of any effusion that appears or worsens during treatment when the measurable tumor has met criteria for response or stable disease is mandatory to differentiate between response or stable disease (an effusion may be a side effect of the treatment) and progressive disease (PD).

5.3 Response Criteria

Response will be based on evaluation of target and non-target lesions. To be assigned a best response of partial response (PR) or complete response (CR), changes in tumor measurements must be confirmed by repeat studies that should be performed at a minimum of 4 weeks after the criteria for response are first met. A best response of SD will not require a confirmatory measurement; however, best overall response of SD will not be assessed unless a patient has received at least 2 complete cycles of treatment.

5.3.1 Evaluation of Target Lesions

Complete Response (CR): Disappearance of all target lesions

Partial Response (PR): At least a 30% decrease in the sum of the longest diameter (LD) of target lesions, taking as reference the baseline sum LD.

Progressive Disease (PD): At least a 20% increase in the sum of the LD of target lesions, taking as reference the smallest sum LD recorded since the treatment started or the appearance of one or more new lesions.

Stable Disease (SD): Neither sufficient shrinkage to qualify for PR nor sufficient increase to qualify for PD, taking as reference the smallest sum LD since the treatment started

5.3.2 Evaluation of Non-Target Lesions

Complete Response (CR): Disappearance of all non-target lesions and normalization of tumor marker level.

Incomplete Response/Stable Disease (SD): Persistence of one or more non-target lesion(s) or/and maintenance of tumor marker level above the normal limits

Progressive Disease (PD): Appearance of one or more new lesions and/or unequivocal progression of existing non-target lesions

Although a clear progression of “non-target” lesions only is exceptional, in such circumstances, the opinion of the treating physician should prevail, and the progression status should be confirmed at a later time by [name] and the UTHSA Data Safety Monitoring Committee assigned to this protocol.

Note: If tumor markers are initially above the upper normal limit, they must normalize for a patient to be considered in complete clinical response.

5.3.3 Evaluation of Best Overall Response

The best overall response is the best response recorded from the start of the treatment until disease progression/recurrence (taking as reference for progressive disease the smallest measurements recorded since the treatment started). The patient's best response assignment will depend on the achievement of both measurement and confirmation criteria (see section 6.4).

Patients with a global deterioration of health status requiring discontinuation of treatment without objective evidence of disease progression at that time should be classified as having “symptomatic deterioration.” Every effort should be made to document the objective progression, even after discontinuation of treatment.

In some circumstances, it may be difficult to distinguish residual disease from normal tissue. When the evaluation of complete response depends on this determination, it is recommended that the residual lesion be investigated (fine needle aspirate/biopsy) before confirming the complete response status.

5.3.4 Endpoint Assessment

The overall response rate (ORR) will be defined as response after scans assessed after two cycles of therapy (1 cycle = 3 weeks). Clinical response will be assessed by the treating physician as outlined above. All patients who are on study after 2 cycles will be considered evaluable for the response endpoints.

Progression-free survival (PFS) will be defined as the time from the first study treatment to the first occurrence of progression or death. All patients who receive at least one dose of each drug will be evaluable for this endpoint.

Toxicity will be assessed NCI CTCAE v 4.03. The incidence, nature, and severity of adverse events will be determined. All patients who receive at least one dose of study drug will be considered evaluable for toxicity and safety endpoints.

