Objectives	
The overall purpose of this study is to determine the overall response rate, efficacy and safety of the combination of Eribulin and Lenvatinib.
 
The primary objectives are:
 
 1. Overall Response rate of the combination at MTD (Phase II) 
Secondary objectives include:
 
 1. Determine the safety of Eribulin and Lenvatinib 2. Define the progression free survival 3. Expression profile of MicroRNA
Patient Population	The number of subjects in the safety run-in phase will be 10. In the phase II trial the number of patients will be 30.
Treatment Plan	This is a phase II clinical trial of the combination of Eribulin, and Lenvatinib. A cycle will be defined as 21 days. Eribulin will be given on days 1 and 8 of each cycle. Lenvatinib will be given daily during each cycle. Eribulin will be given on day 1 and day 8 at 1.4 mg/m ² and lenvatinib at a dose of 20 mg will be started on day 2 for the first ten patients. At that time and based on tolerability the PI will have a teleconference with the EISAI medical team and decide whether to increase the lenvatinib dose to 24mg/day. Then the dose of lenvatinib can increase to 24 mg/day for the remaining cycles.
Efficacy Assessment	Response rate will be measured by performance of imaging after every two cycles of therapy.

Safety
Run- in
Phase

First ten patients treated with Lenvatinib at 20 mg qd
(starting day 2) and eribulin at 1.4 mg/m² day 1 and day
8 of a 21 day cycle

PHASE
II
TRIAL
(30
patients)

Based on toxicity data Lenvatinib
dose may increase to 24 mg daily
and Eribulin at 1.4 mg/m² day 1
and day 8 of a 21 day cycle

Introduction – Background and Rationale

Vascular endothelial growth factor (VEGF) stimulates endothelial cell proliferation and is key to tumor angiogenesis and growth.¹ Targeting VEGF or its receptor (VEGFR) may limit tumor induced angiogenesis, vascular supply to the tumor and halt tumor growth. The therapeutic benefits of this strategy have been proven in several solid tumors including non-small cell lung cancer, colon cancer, and renal cell carcinoma.^{2 3}

The VEGF pathway can be inhibited with monoclonal antibodies against VEGF (e.g. bevacizumab) or the extracellular domain of the VEGFR (e.g. ramucirumab), as well as by several small molecule tyrosine kinase inhibitors targeting VEGFR (e.g. sorafenib, lenvatinib, sunitinib, pazopanib) among others.

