4.0 Treatment plan

4.1 Overview

This will be a phase II, non-randomized trial to determine the efficacy and safety of the combination of Eribulin, and lenvatinib in patients with metastatic breast cancer, non-small cell lung cancer and sarcoma. Treatments will be given in cycles of 3 weeks (21 days) and staging scans(CT Scans) will be performed every 2 cycles. Bone scans and MRI brain will be optional. Toxicity assessment will take place after each cycle.

Eribulin will be administered on cycle days 1 and 8; lenvatinib is an orally administered medication which will be given daily throughout each cycle (on cycle 1 lenvatinib will be started on day 2). On days when both drugs are administered, Eribulin will be administered immediately prior to lenvatinib.

Patients will be followed after treatment discontinuation until disease recurrence or death. An evaluable patient for toxicity is any patient who has received at least 1 dose of any of the study drugs. An evaluable patient for efficacy is any patient who has received at least 2 cycles of therapy.

There will be a safety run-in phase. Ten patients will receive lenvatinib at 20 mg daily and Eribulin at 1.4 mg/m² day 1 and day 8 of a 21 day cycle. Eribulin will be given on day 1 and lenvatinib at 20 mg daily will be started on day 2. After completion of 1 cycle of therapy for the first 10 patients the PI will have a teleconference with the medical team at EISAI and decide whether to continue at the same dose or increase the dose to 24 mg daily of lenvatinib and Eribulin at 1.4 mg/m² day 1 and day 8 of a 21 day cycle.

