6.0 Study Parameters

Procedures	Screening & Baseline	Cycle 1	Every cycle ²	Every 2 cycles or at study termination	End of study visit ⁷	Follow-Up ⁶
Tissue procurement ¹	X			X ⁵		
Informed consent	X					
Eribulin administration			X (Days 1 & 8)			
Lenvatinib			X once daily (starting on day 2 of cycle 1)			
Medical history ³	X		X		X	
Physical exam ³	X		X		X	
CBC w/ diff	X ³		X		X	
Comprehensive chemistry panel	X ³		X			
TSH	X		X			
Serum pregnancy test	X					
EKG	X		X ¹⁰			
Blood draw for micro RNA assay ⁹		X			X	

Procedures	Screening & Baseline	Cycle 1	Every cycle ²	Every 2 cycles or at study termination	End of study visit ⁷	Follow-Up ⁶
Urine analysis ¹¹	X			X		
Imaging ⁸	X ⁴			X		
Toxicity assessment			X			
Biopsy				X ⁵		
Survival status						X

¹Archival tissue or a fresh biopsy will be required to procure tissue for study purposes. Biopsy does not need to be repeated for study purposes if archived tissue is available.

Tissue procurement is voluntary

²A cycle is defined as 3 weeks or 21 days (+/- 3 days). Eribulin will be given on cycle days 1 and 8 and lenvatinib starting on day 2 of cycle one and then continuously.

³Pre-study laboratory tests, medical history, and physical exam (including performance status and review of systems) must be completed within 28 days prior to registration.

Pre-study CBC and CCP will be repeated on day 1 prior to treatment administration.

⁴Pre-study imaging must be performed within 28 days prior to registration.

⁵At the initiation and completion of study treatment (or at the time of early withdrawal), tissue samples should be obtained for correlative studies. This is voluntary and will only be done on patients who consent to it.

⁶Patients will be followed every 6 months, at the time of routine clinic visit or via phone, until death, to document disease progression and survival.

⁷Within 30 days of last dose of study medications.

⁸Imaging modality is left to the discretion of the investigator. However the same imaging modality should be used every two cycles to assess disease status.

⁹Blood samples for microRNA assay will be collected on Cycle 1, Day 1 and at the end of treatment.

¹⁰Repeat EKG with every cycle in patients with congestive heart failure, bradyarrhythmias, or those who are taking drugs known to prolong the QT interval, including Class Ia and III antiarrhythmics.

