8.1.2 Phase II

We will use group of n= 30 patients at the MTD. The expected poor response rate is p=0.20 or less, while p>=0.4 or more would be considered successful/good. We intend to proceed by calculating a response rate and providing a 95% confidence interval in the experimental group. This interval will have an approximate half width 2x [0.5/sqrt(30)]= 0.18 or less. We will test the hypothesis that the response rate is larger than 0.2 in the following way: if the lower bound of the one sided 90% exact confidence interval for underlying p is greater than 0.2, we will consider this evidence that p>0.2 i.e. of good response, and worthy of further investigation. Equivalently, using a one sided exact test of H0: p=0.2 versus H1: p>0.2, with power at p=0.4 being over 80%, we have the power analysis below.

Numeric Results for testing H0: P = P0 versus H1: P > P0

Test Statistic: Exact Test

		Given H0	Given H1	Difference	Target	Actual		Reject H0
Power	N	(P0)	(P1)	(P1 - P0)	Alpha	Alpha	Beta	If R>=This
0.8237	30	0.2000	0.4000	0.2000	0.1000	0.0611	0.1763	10

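### Section 5.3.4 ties ORR to the scan after two cycles with no confirmation stated, 5.3 and 5.3.3 require a confirmed best response until progression, and 8.1.2 does not say which count is R in the R ≥ 10 of 30 rule

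*Combined protocol and SAP*

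**What the plan says.** Overall response rate is the primary objective (section 3.0 and Synopsis). Section 5.3.4 is the only place that defines it: "The overall response rate (ORR) will be defined as response after scans assessed after two cycles of therapy". A cycle is 3 weeks, so this is about week 6. The next sentence reads: "Clinical response will be assessed by the treating physician as outlined above". Neither sentence mentions confirmation.

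Two neighbouring sections set the response rules:

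- Section 5.3: for a best response of CR or PR, tumour changes "must be confirmed by repeat studies that should be performed at a minimum of 4 weeks after the criteria for response are first met".
- Section 5.3.3: "The best overall response is the best response recorded from the start of the treatment until disease progression/recurrence". It adds that assignment depends on confirmation as well as measurement, and refers to a section 6.4 that is in neither the contents list nor the text.

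Other places describe repeated assessment:

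- Synopsis, Efficacy Assessment: "Response rate will be measured by performance of imaging after every two cycles of therapy".
- Section 4.1: staging scans "will be performed every 2 cycles".
- Section 6.0: imaging falls in the column "Every 2 cycles or at study termination".
- Appendix IV: a RECIST measurement form is due every two cycles.

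Section 8.1.2 sets the decision rule: "We will test the hypothesis that the response rate is larger than 0.2 in the following way". It takes N = 30, p0 = 0.20, p1 = 0.40 and rejects at R ≥ 10. It does not define R or refer back to any part of section 5. Section 8.2 does not settle the matter.

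**The concern.** The trial has one primary endpoint and one formal decision rule, and the text supports two ways of counting responders for that rule. The two counts are not nested. A PR at week 6 that has gone by week 12 is a response under 5.3.4 read literally, and a non-response under 5.3 and 5.3.3. A PR first seen at week 12 and confirmed afterwards is the reverse.

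An analyst could defend either count after seeing the data. At the cut-off, one patient classified differently decides whether the combination is called worthy of further study. The error rates in 8.1.2 also describe the trial only if R is counted under the definition for which 0.20 and 0.40 were chosen, and the plan does not say which that is.

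**Working it through.** **Inputs** (section 8.1.2): N = 30, p0 = 0.20, p1 = 0.40, reject if R ≥ 10, one-sided target alpha 0.10, power at p1 over 80%. All figures assume exactly 30 counted patients.

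**Step 1: reproduce the plan's figures.** With R ~ Binomial(30, p):

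- Alpha = P(R ≥ 10 | p = 0.20) = 0.0611 (stated 0.0611).
- Power = P(R ≥ 10 | p = 0.40) = 0.8237 (stated 0.8237).
- At R ≥ 9, alpha would be 0.1287, above 0.10, so 10 is the right cut-off.

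**Step 2: check the confidence-bound form of the rule.** The exact one-sided 90% lower bound for x responders is the 0.10 quantile of Beta(x, 31 − x):

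- x = 10: 0.2184, above 0.20, success.
- x = 9: 0.1899, below 0.20, failure.

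The two forms of the rule agree.

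**Step 3: classify patients under each wording.** Scans fall at about weeks 6, 12, 18 and so on.

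| Course | 5.3.4 read literally | 5.3 with 5.3.3 |
|---|---|---|
| PR at week 6, still PR at week 12 | response | response |
| PR at week 6, lost at week 12 | response | non-response |
| No PR at week 6, PR at week 12, confirmed at week 18 | non-response | response |

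The second and third rows pull R in opposite directions. The documents give no rate for either course, so the net shift cannot be computed and could be zero.

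**Step 4: how much mismatch the rule tolerates.** This needs no assumed rate of late or unconfirmed responses. Solve P(R ≥ 10 | p) for p:

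- Alpha = 0.10 at p = 0.10 quantile of Beta(10, 21) = 0.2184. The margin over p0 is 0.0184, and 0.0184 × 30 = 0.55 expected responder.
- Power = 0.80 at p = 0.80 quantile of Beta(10, 21) = 0.3921. The margin below p1 is 0.0079, and 0.0079 × 30 = 0.24 expected responder.

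**Step 5: why a single shifted alpha should not be quoted.** Suppose, purely as an assumption, that the counted definition yields one expected responder per 30 more, or one fewer, at p1. Alpha then depends on how the shift carries over to p0:

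| Assumed shift at p1 | Power | Alpha, same absolute shift at p0 | Alpha, proportional shift at p0 |
|---|---|---|---|
| +1 per 30 (p1 = 0.4333) | 0.903 | 0.141 (p0 = 0.2333) | 0.096 (p0 = 0.2167) |
| −1 per 30 (p1 = 0.3667) | 0.711 | 0.020 (p0 = 0.1667) | 0.036 (p0 = 0.1833) |

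The proportional p0 values are 0.20 × 0.4333/0.40 and 0.20 × 0.3667/0.40. For the upward shift, alpha exceeds 0.10 under one assumption and not under the other. Nothing in the documents supports a shift of one responder in the first place.

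**The case against.** The best counter-argument is that the sections can be read together. Section 5.3 governs how any CR or PR becomes a best response. Section 5.3.4 comes straight after those rules and points back to them ("Clinical response will be assessed by the treating physician as outlined above"). The Synopsis and sections 4.1 and 6.0 all describe scans every two cycles, so the two-cycle phrase in 5.3.4 may be loose wording for that schedule. Two cycles is also the threshold for being evaluable, which suits a first assessment better than an only one. The plan describes no separate category of unconfirmed response.

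This stands as a possible reading, and it may well be what was meant. It is nowhere stated, however. The pointer back concerns how the physician assesses clinical response, not the time window of ORR. Even if it brings in confirmation, the two-cycle time point still differs from best response until progression. If the time point is loose wording, confirmation is still unstated in 5.3.4.

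Two further objections have force. A cut-off that passes 10 and fails 9 is true of any binary rule and is not itself a flaw. And a plan could consistently keep the two-cycle rate as R, with confirmed best response as supportive. That would require exempting the primary endpoint from the confirmation rule in 5.3, which the protocol does not do, so aligning 5.3.4 with 5.3 and 5.3.3 changes less.

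A reader might infer more than the documents support: that the power table is wrong, that the false-positive rate is really 0.141, or that unconfirmed responses will inflate the result. The table is correct. The figure 0.141 needs an assumed shift of one responder applied equally at p0 and p1. The direction of any net shift is unknown.

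**Conclusion.** The wording on the primary endpoint is contradictory when read literally, and 8.1.2 does not say which count is R. This should be fixed before analysis. Confidence is high on the wording. No claim is made about the size or direction of any effect on the result, which may be nil.

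What can be stated is the tolerance of the rule. It meets its targets only if the null rate under the counted definition is at most 0.218 and the target rate is at least 0.392, that is, within about 0.55 and 0.24 expected responder per 30 of the design values. If 0.20 and 0.40 already refer to the counted definition, alpha 0.0611 and power 0.8237 stand as printed. All of this assumes 30 counted patients; which patients are evaluable is a separate question.

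**What to change.** 1. Reword 5.3.4 so that ORR is the proportion with a best overall response of CR or PR, taken from the scans every two cycles until progression and confirmed at least 4 weeks after first met. State that unconfirmed responses count as non-responses. This is the rule already in 5.3 and 5.3.3.
2. In 8.1.2, name that count as R. Have the sponsor confirm that p0 = 0.20 and p1 = 0.40 were meant for it. If they were set for the two-cycle rate, restate p0, p1, alpha and power, and check that R ≥ 10 of 30 still meets the 0.10 and 80% targets.
3. Report the two-cycle response rate descriptively.
4. Clerical: the section 6.4 reference in 5.3.3 should point to 5.3.

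The cost is a few sentences and one sponsor confirmation. Scans and forms already scheduled supply the data. Readout is somewhat later, since a week-6 response is confirmed on schedule at about week 12. A response first seen at a patient's last scan cannot be confirmed and would not count, and the same may hold when treatment stops within 4 weeks of first response.

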6.0 Study Parameters

Procedures	Screening & Baseline	Cycle 1	Every cycle ²	Every 2 cycles or at study termination	End of study visit ⁷	Follow-Up ⁶
Tissue procurement ¹	X			X ⁵		
Informed consent	X					
Eribulin administration			X (Days 1 & 8)			
Lenvatinib			X once daily (starting on day 2 of cycle 1)			
Medical history ³	X		X		X	
Physical exam ³	X		X		X	
CBC w/ diff	X ³		X		X	
Comprehensive chemistry panel	X ³		X			
TSH	X		X			
Serum pregnancy test	X					
EKG	X		X ¹⁰			
Blood draw for micro RNA assay ⁹		X			X	

Procedures	Screening & Baseline	Cycle 1	Every cycle ²	Every 2 cycles or at study termination	End of study visit ⁷	Follow-Up ⁶
Urine analysis ¹¹	X			X		
Imaging ⁸	X ⁴			X		
Toxicity assessment			X			
Biopsy				X ⁵		
Survival status						X

¹Archival tissue or a fresh biopsy will be required to procure tissue for study purposes. Biopsy does not need to be repeated for study purposes if archived tissue is available.

Tissue procurement is voluntary

²A cycle is defined as 3 weeks or 21 days (+/- 3 days). Eribulin will be given on cycle days 1 and 8 and lenvatinib starting on day 2 of cycle one and then continuously.

³Pre-study laboratory tests, medical history, and physical exam (including performance status and review of systems) must be completed within 28 days prior to registration.

Pre-study CBC and CCP will be repeated on day 1 prior to treatment administration.

⁴Pre-study imaging must be performed within 28 days prior to registration.

⁵At the initiation and completion of study treatment (or at the time of early withdrawal), tissue samples should be obtained for correlative studies. This is voluntary and will only be done on patients who consent to it.

⁶Patients will be followed every 6 months, at the time of routine clinic visit or via phone, until death, to document disease progression and survival.

⁷Within 30 days of last dose of study medications.

⁸Imaging modality is left to the discretion of the investigator. However the same imaging modality should be used every two cycles to assess disease status.

⁹Blood samples for microRNA assay will be collected on Cycle 1, Day 1 and at the end of treatment.

¹⁰Repeat EKG with every cycle in patients with congestive heart failure, bradyarrhythmias, or those who are taking drugs known to prolong the QT interval, including Class Ia and III antiarrhythmics.

¹¹Lenvatinib may cause proteinuria. Patients with 2+ or greater urine dipstick reading should undergo further assessment with a 24-hour urine collection. If 24hr urine protein ≥ 2 g then suspend lenvatinib until it decreases to <2 g and dose reduce by one dose level. If nephrotic syndrome then permanently discontinue lenvatinib.

